Part 2 patients will be enrolled and treated to further characterize safety and preliminary efficacy in a selected cancer patient population with the greatest potential for clinical benefit from FPA144 treatment. Treatment may continue until disease progression, unacceptable toxicity, patient or physician decision to discontinue, death, or termination of the study.

**Study Design
(Cont.):**

Two cohorts of patients with FGFR2b-selected tumors will enroll in Part 2, as follows:

- Cohort A: Approximately 20 patients with gastric cancer with strong FGFR2b overexpression
- Cohort F: Up to 30 patients with FGFR2b-selected non-gastric solid tumors, including patients with FGFR2b-selected bladder cancer. Enrollment of non-gastric tumor types will be contingent on the development of an accompanying validated laboratory test for the analysis of FGFR2b overexpression.

Based on Sponsor discretion, the following cohorts will be closed for enrollment in Part 2:

- Cohort B: Patients with FGFR2b overexpressing gastric cancer in the absence of *FGFR2* amplification
- Cohort C: Patients with gastric cancer without FGFR2b overexpression
- Cohort D: Patients with gastric cancer with moderate FGFR2b overexpression
- Cohort E: Patients with gastric cancer with low FGFR2b overexpression

Study Population:**Inclusion Criteria**

Patients enrolling into Part 1(A or B) or Part 2 must meet ***all*** of the following inclusion criteria:

1. Understand and sign an Institutional Review Board/Independent Ethics Committee-approved informed consent form prior to any study-specific evaluation
2. Life expectancy of at least 3 months
3. ECOG performance status of 0 to 1
4. Age ≥ 18 years at the time the informed consent form is signed except for the patients in Taiwan, where the patient's age must be ≥ 20 at the time the informed consent form is signed.

**Study Population
(Cont.)**

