Pharmacodynamic Assessments:	Tumor biopsies, mandatory as feasible, will be performed before treatment and either at 15 days or 29 days on-treatment for all patients in Part 2 (see Section 6.4). Feasibility at each timepoint will be assessed by the Investigator and should include a consideration of patient safety. Patients may also have an optional on-treatment biopsy upon documented tumor response and/or optional post-treatment biopsy upon documented tumor progression after discussion with the Sponsor.
Statistical Procedures:	
The total enrollment planned for this study was approximately 70–210 patients. Based on the Sponsor decision to close a subset of cohorts in Part 2 (as described in Section 4.1), the planned patient enrollment will be approximately 100 patients.
 
Approximately 20–30 patients will be enrolled into Part 1A. In Part 1B, up to 30 patients with gastric cancer will be enrolled. For Part 2, exploratory activity will be examined by enrollment of:
 
• Cohort A: Approximately 30 patients with gastric cancer with strong FGFR2b overexpression defined as IHC 3+ \geq 10% tumor membrane staining.• Cohort C: Approximately 10-30 patients with gastric cancer without FGFR2b overexpression (IHC 0). Expansion of this cohort to 30 patients will be contingent on Sponsor’s decision to evaluate additional patients without FGFR2b overexpression as a basis for exploring patient selection based on FGFR2b expression.

**Statistical
Procedures
(Cont.):**

The following additional cohorts may be explored in Part 2 at the discretion of the Sponsor:

- Cohort D: Approximately 30 patients with gastric cancer with moderate FGFR2b overexpression defined as IHC 2+ \geq 10% **and/or** IHC 3+ < 10% tumor membrane staining.%. Enrollment in this cohort will be contingent on Sponsor's decision to explore lower IHC score limits.
- Cohort E: Approximately 30 patients with gastric cancer with low FGFR2b overexpression defined as IHC 1+ **and/or** IHC 2+ < 10% tumor membrane staining.%. Enrollment in this cohort will be contingent on Sponsor's decision to explore lower IHC score limits.
- Cohort F: Approximately 30 patients with FGFR2b-selected non-gastric solid tumors, including patients with FGFR2b-selected bladder cancer. Enrollment of additional tumor types will be contingent on the development of an accompanying validated laboratory test for the analysis of FGFR2b overexpression.

List of Key Study Personnel

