enroll approximately 20 patients with gastric cancer with strong FGFR2b overexpression. Cohort F will enroll up to 30 patients for FGFR2b-selected solid tumors outside of gastric cancer, including patients with FGFR2b-selected bladder cancer. Enrollment of additional tumor types in this cohort will be contingent on the development of an accompanying validated laboratory test for the analysis of FGFR2b overexpression. Cohort B, which was defined as the cohort of patients with tumors with FGFR2b overexpression in the absence of *FGFR2* amplification, was closed for enrollment due to the absence of eligible patients (unpublished internal FivePrime data). In addition, Cohort C, planned to enroll patients with gastric cancer without FGFR2b overexpression (IHC score of 0), will be closed. Cohort D, which was defined as the cohort of patients with gastric cancer with moderate FGFR2b overexpression, and Cohort E, which was defined as the cohort of patients with gastric cancer with low FGFR2b overexpression, will also be closed to enrollment.

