4.4 Patient Identification and Enrollment

Patients must be able to provide written informed consent and meet all inclusion criteria and none of the exclusion criteria. No waivers of inclusion or exclusion criteria will be granted by the Investigator and Sponsor or its designee for any patient enrolled in the study. Before enrolling a patient, all eligibility criteria must be satisfied. Patients who qualify for Part 1A of the study will

be enrolled into the first available cohort. In Part 1B, approximately 3 gastric cancer patients may be enrolled at each dose level, starting one dose level below the current Part 1A dose. The Sponsor and Investigators may elect to enroll up to an additional 3 patients per dose level whose tumors overexpress FGFR2b. In Part 2, approximately 20 patients with gastric cancer with strong FGFR2b overexpression (IHC 3+ \geq 10%, Cohort A) will be enrolled. A cohort of patients with FGFR2b-selected non-gastric solid tumors will also be enrolled in Part 2 (Cohort F), including FGFR2b-selected bladder cancer which has an accompanying validated IHC assay. Patients with additional tumor types may be enrolled, contingent on the development of an accompanying validated laboratory test for the analysis of FGFR2b expression.

The Investigator may repeat qualifying lab tests and vitals/ECGs prior to enrollment if a non-qualifying finding is considered an error or an acute finding is likely to meet eligibility criteria on repeat testing.

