8.10 Determination of Sample Size

Three patients per dose group, with a sample size increase to 6 in the case of DLT, is generally accepted as adequate to determine the safety of escalating doses of novel oncologic drugs. If a DLT is observed in 1 of 3 patients, then 3 additional patients will be enrolled at that same dose level. Dose escalation will continue until 2 of 3–6 patients treated at a dose level experience a DLT. The maximum tolerated dose (MTD) is defined as the maximum dose at which < 33% of patients experience a DLT during Cycle 1. After the MTD is determined, additional gastric cancer patients may be recruited at that dose level to further characterize the safety, PK, pharmacodynamics, and preliminary efficacy of FPA144.

In Part 1B, up to 30 patients with gastric cancer with or without FGFR2b overexpression, in the presence or absence of *FGFR2* amplification may be enrolled to explore preliminary long-term safety and PK.

In each of the Part 2 gastric cancer cohorts (Cohorts A, C, D, and E), approximately 30 gastric cancer patients with ranges of FGFR2b overexpression scores (IHC 3+ \geq 10%; IHC 0; IHC 2+ \geq

10% tumor membrane staining **and/or** IHC 3+ < 10%; IHC 1+ **and/or** IHC 2+ < 10%) will be enrolled and treated to further characterize safety and preliminary efficacy. For each cohort, a response rate of $\geq 20\%$ would be considered clinically meaningful. To ensure adequate efficacy, an interim analysis may be performed (with the assumption that a response rate of $\leq 5\%$ would be of no interest in the first stage). Assuming a significance level of 5% and 80% power (Table 5), the required sample size is 29 evaluable patients per cohort. The Sponsor may choose to suspend enrollment if no confirmed response (CR or PR) is observed after the first 10 evaluable patients have either received at least 4 cycles of therapy or have had disease progression, as it is unlikely the response rate would be 20% or more. If a full cohort of 30 patients is enrolled for a group, the precision of the 95% confidence interval for the response rate is within 18%.

Table 6: Parameters of Simon’s 2-stage Design

Targeted Response Rate	Response Rate of No Interest	Overall Sample Size	Sample Size at Stage I	Responses to go to Stage II	Number of Overall Responses
20%	5%	29	10	≥ 1	≥ 4

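### Cohort A is planned at about 20 patients in four places and about 30 in two, and the 5%/80% design that Section 8.10 assigns to it holds at 29 but cannot hold at 20

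*Combined protocol and SAP*

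**What the plan says.** Four places plan for about 20 patients.

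- Synopsis, Study Design: "Cohort A: Approximately 20 patients with gastric cancer with strong FGFR2b overexpression". Section 4.1 lists the cohort in the same terms.
- Section 1.6 says Cohort A will "enroll approximately 20 patients with gastric cancer with strong FGFR2b overexpression".
- Section 4.4: "In Part 2, approximately 20 patients with gastric cancer with strong FGFR2b overexpression" (it names Cohort A).

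Two places plan for about 30.

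- Synopsis, Statistical Procedures: "Cohort A: Approximately 30 patients with gastric cancer with strong FGFR2b overexpression".
- Section 8.10: "In each of the Part 2 gastric cancer cohorts (Cohorts A, C, D, and E), approximately 30 gastric cancer patients".

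Section 8.10 then gives the design for each of these cohorts: "Assuming a significance level of 5% and 80% power (Table 5), the required sample size is 29 evaluable patients per cohort". Table 6 sets a target response rate of 20%, a rate of no interest of 5%, 10 patients in stage I, at least 1 response to continue, and at least 4 responses of 29 overall. For a full cohort of 30 the section adds that "the precision of the 95% confidence interval for the response rate is within 18" per cent. No place gives a cut-off, power or precision for a cohort of 20.

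Two totals bear on the size. The synopsis statistics text and Section 8.10 both put the revised study total at about 100; the synopsis sentence opens "Based on the Sponsor decision to close a subset of cohorts in Part 2 (as described in Section 4.1"). Section 3.1.1 puts Part 2 gastric patients at about 40.

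**The concern.** All six statements are current body text, so sites and readers have two enrolment targets for the main gastric efficacy cohort. The only sample-size justification belongs to the larger one. If 20 is the real size, Section 8.10 credits Cohort A with 80% power that it does not have, and the only stated precision is for a cohort half as large again (30/20 = 1.5). What is at stake is how the Cohort A response rate is justified beforehand and read afterwards.

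**Working it through.** **Inputs.** Section 8.10 and Table 6: p0 = 0.05, p1 = 0.20, stop at 0 responses in the first 10, success at 4 or more. The sidedness of the 5% is not stated; one-sided is what reproduces the plan. Cohort sizes are 29 (Section 8.10) and 20 (the four places above).

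**Formula.** With a stop only at 0/10,

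P(success) = P(X_n ≥ 4) − P(X_10 = 0) × P(X_(n−10) ≥ 4), where X_m is binomial (m, p).

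P(X_10 = 0) is 0.5987 at p = 0.05 and 0.1074 at p = 0.20.

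**Plan's own figure, n = 29.**

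- Alpha = 0.0548 − 0.5987 × 0.0132 = 0.0468 (computed before rounding).
- Power = 0.8596 − 0.1074 × 0.5449 = 0.8011.

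So 5% and 80% are met, and 10/29 is the Simon optimal design for these inputs.

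**Same rule, n = 20.**

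- Alpha = 0.0159 − 0.5987 × 0.0010 = 0.0153.
- Power = 0.5886 − 0.1074 × 0.1209 = 0.5756.

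**Other cut-offs and sizes.**

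| Design | Alpha | Power |
|---|---|---|
| n = 29, ≥4 (Table 6) | 4.7% | 80.1% |
| n = 30, ≥4 | 5.1% | 81.4% |
| n = 20, ≥4 | 1.5% | 57.6% |
| n = 20, ≥3 | 6.9% | 75.9% |
| n = 18, ≥4 | 1.1% | 49.3% |
| n = 22, ≥4 | 2.1% | 64.6% |

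All rows use the 0/10 stop. A search of every futility-only rule with a maximum of 20 patients finds that the highest power with alpha ≤ 5% is 64.8% (look at 16, stop at 2 or fewer, alpha 4.3%). A single stage at 20 also fails: ≥4 gives 1.6% and 58.9%; ≥3 gives 7.5% and 79.4%. The smallest maximum size that meets both targets is 27.

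**Precision at 20.** The exact 95% interval, the type named in Section 8.5, has a half-width of at most 22.8 points (at 10/20). For 4/20, the 20% target, it runs from 5.7% to 43.7%.

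**Do the totals settle the size?** Assume that the October 2016 counts for Cohorts C (10) and E (4) in Section 1.7 are final, that Cohort F fills to 30, and that Part 1 is 27 (19 + 8).

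| Total | A = 20 | A = 30 | Stated |
|---|---|---|---|
| Study: 27 + A + 10 + 4 + 30 | 91 | 101 | about 100 |
| Part 2 gastric: A + 10 + 4 | 34 | 44 | about 40 |

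The study total is nearer to 30. The gastric total falls between the two. With both stated as approximate, neither decides the matter.

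**The case against.** **The consequence is small.** Section 8.7 makes efficacy descriptive, Section 8.9 plans no formal interim efficacy analysis, the 0/10 look is optional, and the Sponsor may close a cohort at any time. No passage applies a 4-of-20 rule, so the 57.6% describes a rule carried over here from Table 6 rather than one the plan states for 20. All of this stands and limits the weight of the point. It does not remove the contradiction: 20 is written as the planned size, not as an early closure, and Section 8.10 names Cohort A among the cohorts that need 29 evaluable patients.

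**About 20 is flexible.** Stretching it to 22 still leaves 64.6% power, and the first workable size is 27. The 29 are also evaluable patients, whereas 20 counts enrolled patients.

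**Stronger readings that the documents do not support.**

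- A reader might infer that 20 is the current size, because the revised enrolment text points to Section 4.1 and both passages giving 30 still describe closed cohorts. But the sentences with that pointer end in a total of about 100, which under the assumptions above is closer to 30. The size is unresolved.
- A reader might infer that the 18-point precision at 30 is wrong, because the worst-case exact half-width is 18.7 points. Section 8.10 does not name its interval, Section 8.5 uses exact intervals only where appropriate, and the worst case is 17.9 points for Wald and 16.8 for Wilson. The statement is not shown to be wrong.
- A reader might infer that Table 6 can simply be kept for Cohort F. Section 8.10 applies it to each tumor type, while Cohort F is capped at 30 across all types, so 29 per type does not fit once a second type enrols.

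**Conclusion.** The point holds as an inconsistency between the stated cohort sizes and the stated design. Table 6 is correct at 29 evaluable patients. At 20, keeping the cut-off of 4 takes power from 80.1% to 57.6%, a loss of 22.5 points, and no 20-patient rule with at most one futility look recovers both 5% and 80%. These figures rest on p0 = 5%, p1 = 20%, a one-sided 5% level and exact binomial calculation. The finding that the size is unresolved does not depend on the enrolment assumptions: six passages disagree and none says which replaces the other. It should be fixed, but it bears only on the justification and interpretation of a secondary, descriptive response rate. The primary safety analysis is not affected.

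**What to change.** State one Cohort A size in the synopsis design text, the synopsis statistics text and Sections 1.6, 4.1, 4.4 and 8.10, and reconcile the figure of about 40 gastric patients in Section 3.1.1 with it.

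- **If 20:** say in Section 8.10 that the 29-patient 5%/80% design and the precision quoted for 30 do not apply to Cohort A. Describe its response rate descriptively, in line with Section 8.7. Give the precision at 20: exact 95% half-width up to about 23 points, and 5.7% to 43.7% for 4/20. If a criterion of at least 4/20 is used, state alpha 1.5% and power 58%.
- **If 30:** correct the four places that say 20. Table 6 then holds for Cohort A at 29 evaluable patients.

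In either case, when Section 8.10 is edited, note that 29 patients per tumor type does not fit a Cohort F of up to 30 across types. Two items are editorial clean-up: Section 8.10 cites Table 5 (laboratory assessments) where it means Table 6, and the synopsis statistics text and Sections 8.9 and 8.10 still treat closed Cohorts C, D and E as open.

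Cost: for 20, wording only, with less favourable stated properties. For 30, wording, plus about 10 more patients (30 − 20) if sites have been enrolling to 20. No new procedures or analyses are needed.

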FPA144 inhibits FGF ligand-stimulated FGFR2b phosphorylation and cell proliferation in cell culture in FGFR2b overexpressing gastric and breast cancer cell lines. FPA144 also inhibits tumor growth in FGFR2b overexpressing gastric and breast xenograft models. In addition, FivePrime has demonstrated *in vitro* that FPA144 mediates antibody-dependent cell-mediated cytotoxicity (ADCC) in cells expressing FGFR2b. The 3 potential mechanisms of action of FPA144 include blocking ligand binding and downstream signaling, decreasing expression of the FGFR2b driver protein and enhancing ADCC.

As FPA144 is a targeted biologic, the clinical development of FPA144 will ultimately be in selected patients with alterations in the FGFR2b pathway that are most likely to respond to this novel agent. The tumor types most relevant to date include gastric and bladder cancer, as well as potentially breast, ovarian, and cholangiocarcinoma. Each of these cancers is in need of new therapeutic options. FPA144, a selective FGFR2b inhibitor, may offer benefit in patients with appropriately selected tumors, with an improved safety profile relative to less or non-targeted therapeutics.

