- **Low FGFR2b Overexpression:** defined by the extent of membranous staining in tumor cells giving rise to H-score of ≥ 10 , but < 20 in a sample

The H-score is a method of assessing the extent of membranous immunoreactivity and is derived using the formula: 3 x the percentage of tumor cells with strong membranous staining (3+) + 2 x the percentage of tumor cells with moderate membranous staining (2+) + percentage of tumor cells with weak membranous staining (1+), giving a range of 0 to 300.

For other FGFR2b-selected tumor types outside of gastric and bladder cancer, criteria for defining FGFR2b overexpression will be determined upon availability of a validated assay for each individual tumor type in question. Criteria for determining FGFR2b overexpression will be based on preclinical data and may differ between tumor types.

For determining *FGFR2* gene amplification by FISH, samples submitted for Part1B will be analyzed either prospectively or retrospectively, while samples submitted for Part 2 will be analyzed retrospectively. For this study, a tumor will be considered *FGFR2* gene amplified if the ratio of the *FGFR2* probe to the centromeric probe (CEN10) is ≥ 2 in $\geq 10\%$ of the cells, or there are small clusters of amplification in which the ratio cannot be determined (Su 2014).

A total of 8 patients with gastric cancer with or without FGFR2b overexpressing tumors and with or without *FGFR2* amplification were enrolled in Part 1B (which is closed to enrollment). Two cohorts of patients with FGFR2b-selected tumors will continue enrolling in Part 2. Cohort A will

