3.1.1 Screening Period

All patients will undergo screening assessments within 4 weeks prior to the first dose of FPA144, with the exception that FGFR2b overexpression may be determined by the central laboratory at any time prior to enrollment in the study (*Part 1B and Part 2 patients*).

Tumor tissue for FGFR2b expression analysis will be submitted for Part 1A patients if available for retrospective analysis, and is mandatory for all patients enrolling in Part 1B and Part 2 of the study. In Part 1B, 8 patients with gastric cancer were enrolled, whose tumor tissue was analyzed for FGFR2b expression and *FGFR2* amplification. In Part 2, approximately 40 patients with gastric cancer will be enrolled based on prospective IHC analysis of FGFR2b expression. In addition, up to 30 patients with FGFR2b-selected non-gastric solid tumors (including patients with FGFR2b-selected bladder cancer for which a validated IHC assay is available) will be enrolled based on prospective FGFR2b analysis. Additional non-gastric solid tumor types, aside from bladder cancer, can be enrolled only upon availability of an accompanying validated laboratory test for the analysis of FGFR2b expression.

Study-procedure-related AEs that occur after signing of the informed consent form and before administration of the first FPA144 dose will be collected during this period.

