4.1 Planned Number of Patients and Study Centers

Part 1A (Dose Escalation): A total of 19 patients with locally advanced or metastatic solid tumors were enrolled.

Part 1B: A total of 8 patients with gastric cancer with or without FGFR2b overexpression, in the presence or absence of *FGFR2* amplification, were enrolled.

Enrollment in Part 1(A and B) is closed as the RD for Part 2 has been determined.

Part 2 (Dose Expansion): Part 2 is open for enrollment into the following cohorts:

- Cohort A: Approximately 20 patients with gastric cancer with strong FGFR2b overexpression.
- Cohort F: Up to 30 patients with FGFR2b-selected non-gastric solid tumors (including bladder cancer for which an accompanying validated IHC assay is available). Enrollment of additional tumor types will be contingent on the development of an accompanying validated laboratory test for the analysis of FGFR2b overexpression.

The following cohorts will be closed for enrollment in Part 2:

- Cohort B: Patients with gastric cancer with FGFR2b overexpression without FGFR2 amplification
- Cohort C: Patients with gastric cancer without FGFR2b overexpression
- Cohort D: Patients with gastric cancer with moderate FGFR2b overexpression
- Cohort E: Patients with gastric cancer with low FGFR2b overexpression

The study will be conducted at up to 35 investigational centers globally.

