For Part 2 Cohort F, enrollment of patients with non-gastric solid tumors, including FGFR2b-selected bladder cancer, will be guided by the same 2-stage design used for cohorts A, C, D, and E for each tumor type.

However, the Sponsor may choose to close enrollment of a cohort at any time (Section 9.11). Based on Sponsor decision to close a subset of cohorts in Part 2 (as described in Section 4.1), the planned patient enrollment will be approximately 100 patients.

9. Ethical, Legal, and Administrative Aspects

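### If a second tumor type opens in Cohort F and completes stage I, the shared total of about 30 cannot also supply the 29 evaluable patients that Section 8.10 sets for each type

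*Combined protocol and SAP*

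**What the plan says.** For the gastric cohorts, Section 8.10 takes a 5% response rate as of no interest and 20% as the target, and concludes that "the required sample size is 29 evaluable patients per cohort". Table 6 gives the rule: 10 patients in stage I, at least 1 response to go on, 29 overall, at least 4 responses in total. For Cohort F, the same section says enrollment "will be guided by the same 2-stage design used for cohorts A, C, D, and E for each tumor type".

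The size of Cohort F is always one figure across tumor types:
- Section 4.1: "Cohort F: Up to 30 patients with FGFR2b-selected non-gastric solid tumors".
- Section 3.1.1: "up to 30 patients with FGFR2b-selected non-gastric solid tumors (including patients with FGFR2b-selected bladder cancer for which a validated IHC assay is available".
- Section 1.6: "up to 30 patients for FGFR2b-selected solid tumors outside of gastric cancer".
- Synopsis, Study Design: also up to 30.
- Synopsis, Statistical Procedures: "Cohort F: Approximately 30 patients with FGFR2b-selected non-gastric solid tumors".

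Section 4.1 allows further tumor types once a validated assay exists. Section 1.1 indicates candidates: "The tumor types most relevant to date include gastric and bladder cancer, as well as potentially breast, ovarian, and cholangiocarcinoma". No section divides the places among types, or says which size and threshold apply to a type that ends between 10 and 29 evaluable patients.

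**The concern.** The sample size rule is written per tumor type, while the places are counted per cohort. The two agree only while one type is enrolling. A per-type rule serves a purpose only if more than one type can enroll, and Section 4.1 provides for that.

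What is at stake is the reading of response by tumor type, a secondary objective in Section 2.2. Pooling the types is not an obvious substitute, because Section 1.6 adds: "Criteria for determining FGFR2b overexpression will be based on preclinical data and may differ between tumor types". If two types enroll, a reader of Section 8.10 would credit each with a 29-patient evaluation at 5% and 80%, and the total cannot provide that. A share or threshold chosen after responses are known would also make any per-type go/no-go decision harder to interpret.

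**Working it through.** **Inputs.** Rate of no interest p0 = 0.05, target p1 = 0.20, stage I n = 10 (continue if at least 1 response), overall n = 29 (at least 4 responses), all from Section 8.10 and Table 6. Cohort F total = 30, from Sections 1.6, 3.1.1 and 4.1 and the synopsis. The plan does not state sidedness; the 5% is taken as one-sided.

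**1. The plan's own design.** The probability of declaring success at true rate p is the sum over x = 1 to 10 of P(X1 = x) × P(X2 ≥ 4 − x), with X1 ~ Bin(10, p) and X2 ~ Bin(19, p).
- p = 0.05: 0.0468
- p = 0.20: 0.8011

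The stated 5%, 80% and 29 all reproduce.

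**2. Could a smaller size carry the same properties?** Keeping the rule of at least 1 in 10 and trying every overall size from 11 to 31 with every threshold, only 29 meets alpha ≤ 0.05 and power ≥ 0.80. Its neighbours at the ≥4 threshold:

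| n | alpha | power |
|---|---|---|
| 28 | 0.0426 | 0.7862 |
| 29 | 0.0468 | 0.8011 |
| 30 | 0.0513 | 0.8141 |

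Over all one-stage and two-stage rules the smallest size is 27 (one stage, ≥4: 0.0437 and 0.8177). Two types would then still need 2 × 27 = 54.

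**3. Evaluable patients needed against 30 enrolled places.**

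| Situation | Evaluable patients needed |
|---|---|
| One type, full design | 29 |
| Two types, stage I only | 10 + 10 = 20 |
| Three types, stage I only | 3 × 10 = 30 |
| One full design plus one stage I | 29 + 10 = 39 |
| Two full designs | 2 × 29 = 58 |

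The left side of the comparison counts evaluable patients and the 30 counts enrolled patients. Section 8.1.3 requires, among other things, a post-baseline assessment for efficacy evaluability. The first row therefore fits a total of exactly 30 only with at most 30 − 29 = 1 non-evaluable patient, and the three-type row only with none. Non-evaluable patients make the last two rows worse.

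**4. How likely is the shortfall once two types have completed stage I?** At least 20 places are used and at most 10 remain, while continuing either type needs 29 − 10 = 19 more. P(0 of 10) = 0.95^10 = 0.5987 at a 5% rate and 0.80^10 = 0.1074 at 20%. If Table 6 is followed, so that any response means continuing, the chance that at least one of two types continues is:
- both true rates 5%: 1 − 0.5987² = 0.64
- one 5%, one 20%: 1 − 0.5987 × 0.1074 = 0.94
- both 20%: 1 − 0.1074² = 0.99

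The true rates here are assumptions chosen to span the plan's two reference values.

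**The case against.** The strongest reply is that nothing conflicts in the study as it is now running. Bladder is the only non-gastric type with a stated assay (Sections 3.1.1 and 4.1) and the only one reported as enrolling (Section 1.7). Other types wait on an assay, and Section 1.1 is background that calls them only potentially relevant. The rule is also permissive: the design guides, the interim look is optional, and the sponsor may close a cohort at any time (Sections 8.9, 8.10 and 9.11). Efficacy is descriptive (Section 8.7), and exact confidence intervals are planned where appropriate (Section 8.5).

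All of this stands and sets the weight of the point. None of it supplies the missing statement, since even a guide should not attach a size and power to each type that the cohort total cannot deliver.

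A reader might infer more than the documents support:
- *That the sizes fail as soon as a second type opens.* They do not. A second type closed after a single patient still leaves 29 + 1 = 30, provided every patient is evaluable.
- *That every type needs 29.* A type that stops at 0 of 10 has completed the design.
- *That the smaller types have some particular low power.* The plan gives no threshold for a type ending below 29, so any such figure would rest on a rule the plan does not contain.
- *That a response in stage I obliges the sponsor to go on.* Section 8.10 permits suspension at 0 of 10 and leaves the sponsor free to close a cohort, so the probabilities in step 4 describe the design when followed.

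**Conclusion.** The point holds, conditionally and at low severity. Once a second type has completed stage I, a full design in the other needs at least 39 evaluable patients against about 30 enrolled, and two full designs need 58. The 29-patient size and its 5%/80% properties can then hold for at most one type. Reading the total as approximate does not help: 39 is 30% above it.

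This rests on three things: a second type opening and reaching 10 evaluable patients, the total being shared as every section that gives it says, and the 10 and 29 being evaluable patients. No confirmatory test is affected, and the documents give no ground for saying that Cohort F is invalid or that bladder cancer cannot be evaluated as planned.

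**What to change.** Keep the total of 30 and the optional check for 0 responses after 10 evaluable patients in each type. Restate Section 8.10 and the Cohort F bullet of the synopsis to say that:

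1. The 30 enrolled places are shared across all non-gastric tumor types.
2. The stage II size of 29 evaluable patients, the threshold of 4 responses and the 5%/80% properties apply only to a type that actually reaches 29 evaluable patients, which the total allows for at most one type.
3. Any type ending below 29 is reported descriptively with the exact 95% confidence interval of Section 8.5, and no error-rate claim is made for it.

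The text should not state how many places remain after one type finishes, because that would treat evaluable and enrolled patients as the same. Naming a priority type, or setting sizes and thresholds for smaller types, is optional and for the sponsor.

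The cost is a few sentences and no added patients. The downside is a weaker stated claim for smaller types: 3 of 15 has an exact 95% interval of 4% to 48%, and 0 of 10 has an upper limit of 31%, so a stage I stop alone does not exclude a 20% rate. By the counts in Section 1.7, Cohorts A, C and E (12 + 10 + 4) account for all 26 Part 2 patients dosed by the October 2016 cut-off. At that date the wording could still be settled before any Cohort F response was seen.
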